9 SUBJECT POPULATIONS

9.1 Enrolled Set

The Enrolled Set includes all subjects with a signed (by subject, parent(s) or legal guardian(s) as appropriate) informed consent form and if required by local law an assent form.

9.2 Allocated Set

The Allocated Set includes all subjects who are allocated to treatment.

Analysis of the Allocated Set will be conducted according to the allocated treatment.

9.3 Safety Set

The Safety Set (SAF) includes all treated subjects, i.e., all subjects in whom IMP was administered (at least once).

The analysis on the SAF will be conducted on the actual treatment received.

9.4 Full Analysis Set

The Full Analysis Set includes all allocated and treated subjects, i.e., all allocated subjects who were administered any amount of IMP.

The FAS is the primary analysis set, i.e., the analysis set used for the conduct of the primary analysis of this trial.

The analysis on the FAS will be conducted according to the allocated treatment.

9.5 Per Protocol Set

The Per Protocol Set defines a subset of the subjects in the Full Analysis Set without any major protocol deviation affecting the primary endpoint. As the Per Protocol Set is only relevant for analyses during Part 1, no protocol deviation during Part 2 yields to exclusion from the Per Protocol Set.

The impact of a deviation on the efficacy assessment will be assessed by the sponsor during clinical review on a case by case basis prior to database lock. The decision will be documented in the final statistical review.

The analysis on the PPS will be conducted according to the allocated treatment.

9.6 Pharmacokinetic Analysis Set (PK-Set)

All subjects who have quantifiable serum concentrations (i.e., serum concentrations above the lower limit of quantification) during the Treatment Period will be included in the descriptive pharmacokinetic analysis.

Data from subjects who vomit within 6 hours of administration of IMP during the Treatment Period will be carefully assessed to decide if the data should be included in the pharmacokinetic analysis.

9.7 Application of analysis sets

[Table 5](#) shows the use of analysis sets in different analyses.

As SAF and FAS are expected to be identical, the analysis of demographics and baseline characteristics, including medical history and prior and concomitant medication, will only be presented for the SAF. In case of differences resulting in a need for an additional presentation for the FAS, the analysis will be provided as an additional analysis.

Demographics and other baseline characteristics are planned for SAF in PK Set. In case these two analysis sets coincide, presentations will only be prepared for the SAF.

Table 5: Use of analysis sets

	Enrolled Set	Allocated Set	SAF	FAS	PPS	PK Set
Subject disposition	X	X	X	X	X	X
Subject discontinuations			X			
Protocol deviations			X			
Demographics	X		X			X
Other baseline characteristics			X			X
Subject medical history			X			
Previous and concomitant medication			X			
Exposure			X			
Compliance				X		
Serum concentrations and pharmacokinetics						X
Primary endpoint				X		X
Other efficacy endpoints				X		
Secondary safety endpoints			X			
Other safety parameter			X			

10 DISPOSITION

Details on the programming aspects regarding disposition can be found in Section [18.1.4](#).

10.1 Subject disposition

All presentations for subject disposition will be as described in Section [8.1](#). For all Periods, descriptive summaries will also be presented overall.

For describing the subject disposition, the following populations will be summarized for each of the three different trial periods if applicable:

- Subjects enrolled (only overall for Treatment Period).
- Subjects enrolled but not allocated and reason for non-allocation (only overall for Treatment Period).
- Subjects allocated (Treatment Period only).
- Subjects allocated but not treated and reason for not being treated (Treatment Period only).
- SAF.
- FAS.
- PPS (Treatment Period only).
- PK-Set (Treatment Period only).
- Trial completers.
- Treatment completers (not applicable for Observation Period).

- Subjects allocated and discontinued the trial.
- Subjects allocated and discontinued IMP (not applicable for Observation Period).
- Subjects who discontinued Tapentadol Period and entered Observation Period (Tapentadol Period only).

For subjects enrolled, subjects enrolled but not allocated and for the reasons for not being allocated, the percentage denominator will be the number of enrolled subjects. For all other calculations, the percentage denominator will be the number of allocated subjects.

For the Tapentadol and Observation Period, the information will be presented based on the subjects in the SAF entering these periods. The percentage denominator will be the corresponding number of subjects in the SAF.

In addition, subject disposition will be presented for the subgroups as specified in [Table 4](#).

Furthermore, an overview table will be prepared presenting the number of subjects enrolled, allocated, allocated and treated, in the SAF, in the FAS and the PK-Set per country. Percentage calculation will be done in 2 ways:

- Denominator will be the number of all allocated subjects.
- Denominator will be the number of allocated subjects in the respective country.

Reasons for exclusion from the analysis populations will be summarized. The percentage denominator will be the number of subjects allocated.

10.2 Subject discontinuations

Part 1

Discontinuations from the trial and from IMP will be presented for the SAF overall, per country and per site.

Reasons for discontinuations from the trial and from IMP will be presented for

- Subjects discontinued from the trial.
- Subjects discontinued from IMP.

Percentage denominator will be the number of subjects discontinuing in the respective arm.

Part 2

Discontinuations from the trial will be shown for all subjects entering part 2. Discontinuation from IMP will be presented for all subjects entering the Tapentadol Period. Presentation will be done overall, per country and per site.

Reasons for discontinuations from the trial and from IMP will be presented for:

- Subjects entering Part 2 and discontinued the trial.
- Subjects entering the tapentadol period of Part 2 and discontinued IMP.

Percentage denominator will be the number of subjects discontinuing in the respective arm.

Part 1 and Part 2

The details for “other reasons” will be presented in a listing sorted by site and treatment, if applicable.

If more than 10% of subjects in the SAF per treatment group of Part 1 discontinue the IMP in the Treatment Period or if more than 10% of subjects entering the Tapentadol Period discontinue the IMP in the Tapentadol Period respectively, the distribution of the time to discontinuation from IMP will be summarized using time-to-event methods. Time will be in days until discontinuation for Part 1 and in weeks until discontinuation for the Tapentadol Period. For the Tapentadol Period, a graphical display using Kaplan-Meier methods displaying subjects at risk per time-point will also be produced.

The calculation of time to IMP discontinuation and the censoring algorithm are described in Section [18.1.4.1](#).

If more than 10% of subjects in the SAF per treatment group of Part 1 discontinue the IMP in the Treatment Period or if more than 10% of subjects entering the Tapentadol Period discontinue the IMP in the Tapentadol Period due to lack of efficacy, the time to discontinuation due to lack of efficacy will be calculated and evaluated as described above only for subjects who discontinued due to lack of efficacy. Additionally to the censoring algorithm described in Section [18.1.4.1](#), subjects who discontinue IMP for reasons other than lack of efficacy will be censored at the time of discontinuation.

If more than 10% of the subjects in the SAF per treatment group of Part 1 discontinue IMP in the Treatment Period or if more than 10% of the subjects entering the Tapentadol Period discontinue the IMP in the Tapentadol Period due to an adverse event (AE), time to discontinuation due to AEs will be calculated and evaluated as described above only for subjects who discontinued due to AEs. Additionally to the censoring algorithm described in Section [18.1.4.1](#), subjects who discontinue the IMP for reasons other than AE will be censored at the time of discontinuation.

If more than 10% of subjects in the SAF per treatment group of Part 1 discontinue IMP in the Treatment Period or if more than 10% of subjects entering the Tapentadol Period discontinue the IMP in the Tapentadol Period due to no more need for opioid treatment, the time to discontinuation due to no more need for opioid treatment will be calculated and evaluated as described above. Additionally to the censoring algorithm described in Section [18.1.4.1](#), subjects who discontinue IMP for other reasons will be censored at the time of discontinuation.

All discontinuation data will be presented in a subject data listing sorted by site and treatment.

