8.1.3 Other endpoints

Other endpoints compared between treatment groups at each measurement time point are:

Part 1 - Treatment Period, other endpoints (baseline is the value at Visit V2):

- Pain as assessed by changes from baseline using the VAS.
- Pain as assessed by changes from baseline using the FPS-R.
- Use of rescue medication as assessed by number of doses of rescue medication taken at different dose levels of IMP.
- Description of population pharmacokinetics of tapentadol and tapentadol-O-glucuronide.
- Palatability and acceptability as assessed by differences within treatment groups of the 5-point hedonic faces scale with the verbal rating score at Visit V3 and Visit VE.

Part 2 - Tapentadol Period, other endpoints (baseline is the value at Visit VE):

- Pain as assessed by changes from baseline using the VAS.
- Pain as assessed by changes from baseline using the FPS-R.
- Constipation as assessed by changes from baseline of total scores for the modified CAS.

Part 2 - Observation Period, other endpoints (baseline is the value at Visit VE or Visit ET):

- Constipation as assessed by changes from baseline of total scores for the modified CAS.

Part 1 or Part 2 - other endpoints:

- Opiate withdrawal symptoms as assessed by the scale score of the SOWS questionnaire at individual time points and changes to baseline.
- Time to discontinuation of IMP assessed by a survival analysis.

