14.2.6.4 Time to discontinuation

A survival analysis of the time to discontinuation of IMP overall, due to lack of efficacy, and due to TEAE will be performed for tapentadol PR and morphine PR for Part 1 (Treatment Period) and for tapentadol PR during the Tapentadol Period of Part 2 if at least 10% of the subjects per group discontinue.

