7 DOCUMENT AND CHANGE HISTORY

7.1 Changes in analysis compared to the trial protocol

Not applicable.

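### SAP 10.2 ties the 10% trigger for the adverse-event and lack-of-efficacy time-to-discontinuation analyses to that specific reason; Protocol 14.2.6.4 uses one trigger without a reason, and SAP 7.1 declares no change

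*SAP*

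**What the plan says.** Protocol 8.1.3 lists the endpoint among the other endpoints: "Time to discontinuation of IMP assessed by a survival analysis". Protocol 14.2.6.4 says when it is analysed. It names three analyses together: "A survival analysis of the time to discontinuation of IMP overall, due to lack of efficacy, and due to TEAE will be performed". One condition follows for both Part 1 arms and for the Tapentadol Period: "for tapentadol PR during the Tapentadol Period of Part 2 if at least 10% of the subjects per group discontinue". No reason for stopping is attached to it.

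SAP 10.2 writes a separate condition for each analysis and changes at least 10% to more than 10%.

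- **Overall:** the condition is discontinuation with no reason given. Once more than 10% "discontinue the IMP in the Tapentadol Period respectively, the distribution of the time to discontinuation from IMP will be summarized using time-to-event methods".
- **Lack of efficacy:** the Tapentadol Period clause counts only stops for that reason: "subjects entering the Tapentadol Period discontinue the IMP in the Tapentadol Period due to lack of efficacy, the time to discontinuation" is then calculated.
- **Adverse event:** same structure, ending in "time to discontinuation due to AEs will be calculated and evaluated as described above only for subjects who discontinued due to AEs".

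In the two reason-specific sentences the Part 1 clause comes first, and the reason appears only after the Tapentadol Period clause. The Part 1 threshold can therefore be read with or without the reason. Under SAP 7.1, the section for changes from the protocol, the whole entry is "Not applicable".

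**The concern.** The two documents give different rules for the same protocol-planned analyses, and the difference is not declared. Someone programming from the SAP could leave out the adverse-event or lack-of-efficacy analysis when the protocol calls for it, and would leave it out because the event it describes was infrequent. A low rate of stopping for adverse events is itself a result worth showing, and Part 2 exists to describe long-term safety.

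Neither document says whether one or both Part 1 arms must reach the threshold. If both must, and the Part 1 clause is read with the reason attached, an imbalance between the arms could itself prevent the comparison of timing.

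**Working it through.** **Group sizes.** Protocol 14.1 requires 69 subjects at 2:1, so 46 on tapentadol PR and 23 on morphine PR. As a check, 80% responders in both arms, a 20% margin and one-sided alpha 0.1 give a Farrington-Manning power of 0.784 by the asymptotic formula and 0.808 by exact binomial calculation, so 69 is consistent with the stated 80%. It is used here only for the arm sizes. The documents give no number entering the Tapentadol Period and no stop rates by reason. Those are assumptions below.

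**Smallest count that meets each wording.** At least 10%: k = ceil(0.1n). More than 10%: k = floor(0.1n) + 1.

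| n | at least 10% | more than 10% |
|---|---|---|
| 46 | ceil(4.6) = 5 | 4 + 1 = 5 |
| 23 | ceil(2.3) = 3 | 2 + 1 = 3 |
| 30 | ceil(3.0) = 3 | 3 + 1 = 4 |

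The two wordings differ only when n is a multiple of 10. In Part 1 at the planned size they are identical.

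**Tapentadol Period, where the SAP wording is clear.** Assume n = 30 and 50% stopping, and treat all who enter as one group, as SAP 10.2 does. With X ~ Bin(n, q), the chance that a trigger is met is P(X ≥ k).

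- Protocol: q = 0.50, k = 3, P ≈ 1.0.
- SAP, by reason: q = 0.50 × the reason's share of stops, k = 4.

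| Share of stops | q | SAP trigger met (k = 4) | Same, if at least 10% (k = 3) |
|---|---|---|---|
| 10% | 0.05 | 0.06 | 0.19 |
| 20% | 0.10 | 0.35 | 0.59 |
| 30% | 0.15 | 0.68 | 0.85 |
| 50% | 0.25 | 0.96 | 0.99 |

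The last column adds P(X = 3), which is 0.127, 0.236, 0.170 and 0.027 in turn. At n = 30 the strict inequality contributes part of the shortfall. At shares of 10% and 20%, most of it comes from counting only the named reason.

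Other assumed sizes, still at 50% stopping and for the same four shares, give 0.08, 0.32, 0.60 and 0.91 at n = 20, and 0.05, 0.37, 0.74 and 0.98 at n = 40. The protocol trigger stays near certain: even with n = 20 and 30% stopping it is met with probability 0.992.

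**Part 1.** SAP 7.2.2 calls the rate of discontinuation in the Treatment Period very low, without a figure. At an assumed 5% for any reason, the trigger is met with probability 0.08 on tapentadol PR (5 of 46) and 0.11 on morphine PR (3 of 23). Both arms meet it with probability 0.08 × 0.11 ≈ 0.008, and at least one with 1 − 0.92 × 0.89 ≈ 0.18. The overall condition itself would then usually fail, so neither rule would usually produce the analysis.

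**The case against.** The strongest reply is that little is lost. SAP 10.2 tabulates reasons for discontinuing trial medication without any threshold and lists all discontinuations. SAP 15.1.2.1 counts subjects whose TEAE led to discontinuation, and SAP 15.1.2.2 lists those events. Only the timing analysis is conditional, for an endpoint ranked below the primary and main secondary ones. This stands, and it limits the consequence: an imbalance in stops for adverse events would still be visible.

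It can also be said that a minimum-event condition is sensible at this sample size, and that the protocol's own trigger depends on an outcome too. Both are fair. The point is the undeclared difference between the documents, not the existence of a threshold. Likewise, Protocol 8.1.3 without a condition and 14.2.6.4 with one are ordinary layering, not two competing rules.

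Finally, the any-reason reading of Protocol 14.2.6.4 is inferred. That is correct, but one condition placed after three analyses, with no reason named, is hard to read otherwise.

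**Conclusion.** The discrepancy is real. It is clear for the Tapentadol Period and a matter of ambiguous wording for Part 1. Following SAP 10.2 may drop the adverse-event or lack-of-efficacy analysis when the protocol's condition is met. Under the assumed 30 subjects and 50% stopping, the chance that the SAP trigger is met runs from 0.06 to 0.96 depending on the reason's share of stops, against near certainty under the protocol.

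A reader might infer that these analyses will mostly not be run. The documents do not support that. They give no rates by reason, and under these assumptions the statement is true at shares up to about 20% and false at 30% or more. SAP 7.2.1 says that no longer needing opioids is one of the main reasons for stopping in Part 2, which suggests smaller shares for the other reasons but does not fix them.

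A reader might also build the case on the Part 1 arm sizes. For example, if 13% on tapentadol PR and 4% on morphine PR stop for adverse events, a reason-specific trigger is met in both arms with probability only 0.05. The same scenario gives 0.75 if either arm suffices, the Part 1 clause may not carry the reason at all, and such rates are assumptions that sit uneasily with a rate described as very low. The difference between at least and more than 10% has no effect at 46 and 23.

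**What to change.** In SAP 10.2, replace the separate conditions with the protocol's single one, at least 10% discontinuing trial medication for any reason, and apply it to the overall and all reason-specific analyses in both parts. State whether one or both Part 1 arms must reach it. If the sponsor prefers a reason-specific rule, SAP 7.1 should declare it as a change and justify it, and the Part 1 clause should say which stops are counted. Removing every threshold would be a further departure from Protocol 14.2.6.4 and is not needed.

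In the same edit, correct the instruction that confines the lack-of-efficacy and adverse-event analyses to subjects who stopped for that reason. It conflicts with the sentence after it in each case, which censors subjects who stopped for other reasons.

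The cost is SAP wording and a few extra tables. The small downside is that some curves will rest on few events.

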7.2 SAP amendment rationale

7.2.1 Amendment 02

Amendment 02 to the final SAP was prepared to add a few additional analyses and refine some definitions and programming specifications:

1. Additional analyses:

- Analysis for the time to discontinuation from treatment due to “no more need for opioid treatment” during the Tapentadol Period was added, as this is one of the main reasons for discontinuation of treatment of Part 2.
- Summary statistics for the underlying diagnosis/reason for the pain leading to enrollment of the subjects in the trial.
- For all subjects, irrespective of age, one analysis of the primary endpoint based on VAS and one analysis based on FPS-R.
- Subgroup analyses of the primary endpoint for subjects with and without a neuropathic pain component to assess the effect of treatment depending on the type of the underlying pain.
- Overview of the individual response criteria to get a complete picture of reasons for subjects being responder or non-responder.

2. Programming specifications:

- Additional specifications to handle missing data were added:
 - If the time of the first IMP intake is missing, it will be imputed (by 0:00 in case of morning intake or 12:00 in case of evening intake) to derive the time from first IMP intake to first rescue medication intake.
 - In case of a missing intermediate visit during the Tapentadol Period, the visit date will be imputed to derive the average daily dose for the time frame between two scheduled consecutive visits.
 - In case of missing baseline pain intensity for the Tapentadol Period in the eCRF, the last available pain intensity value from the Treatment Period provided in the eDiary will be used as baseline.
 - Missing baseline pain intensities for the Treatment Period will be imputed using the multiple imputation that is used to impute the missing pain intensity values during the last 3 days of treatment.
- Consideration of deviations from the protocol with respect to the time point of visits in relation to IMP intakes:

- Protocol Amendment 02 specifies that subjects should receive their first IMP intake within 24 hours after randomization and that Day 1 is defined as the day of first IMP intake. Therefore, the definition of Day 1 of the trial in the SAP was updated accordingly to ensure clarity and consistency in the specification of Day 1. For the definition of the treatment completers, this redefined Day 1 of the trial will be considered.

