Summary statistics

Data collected in this trial will be summarized according to their nature as follows:

- Continuous variables: number of non-missing observations, arithmetic mean, standard deviation (SD), minimum and maximum values, median and quartiles. If there are less than 5 observations descriptive statistics will be presented based on the rules specified in Section 18.1.2.2.
- Categorical variables: absolute and relative frequencies. If not defined otherwise, the percentage denominator will be the number of subjects in the trial at the respective time point in the analyzed population.

- Time-to-event variables: Kaplan-Meier estimates together with the 95% confidence intervals (CI) will be provided with the respective number at risk and the number censored at the relevant time points. In addition, the median time-to-event and its 95% confidence interval for all arms will be presented. For calculating the survival estimate CI bounds, the log-log transformed estimate of CI bounds will be used. Censoring mechanisms depend on the specific endpoint and will be described in the respective section.

Details on rounding and presentation in case of missing data can be found in Section [18.1.2](#).

Coding of eCRF-entries

All Medication and additional therapies/treatments will be coded using the World Health Organization Drug Dictionary (WHO-DD) or in case of non-medicinal therapies via Medical Dictionary for Regulatory Activities (MedDRA). The versions of these reference documents will be specified on the appropriate statistical outputs.

All investigator-reported terms for medical history in the electronic case report form (eCRF) and all original terms used by the investigators in the eCRFs to identify adverse events (AEs) will be coded using the Medical Dictionary for Regulatory Activities (MedDRA).

For the final analyses, the latest version of the WHO-DD/MedDRA at the time of coding for final evaluations will be used. These might be different for the final analyses of Part 1 and the final analysis of Part 2. Coding for the DMC analyses is addressed in the DMC SAP.

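### SAP 10.2 contradicts itself on who is analysed for time to discontinuation by reason, and Kaplan-Meier with other stops censored overstates those proportions, mainly in the Tapentadol Period

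*SAP*

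**What the plan says.** Protocol 14.2.6.4 plans the analysis in general terms: "A survival analysis of the time to discontinuation of IMP overall, due to lack of efficacy, and due to TEAE will be performed". It covers Part 1 and the Tapentadol Period and depends on a 10% threshold. Protocol 8.1.3 lists time to discontinuation among the other endpoints.

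SAP 8.1 fixes the estimator: "Time-to-event variables: Kaplan-Meier estimates together with the 95% confidence intervals (CI) will be provided", together with numbers at risk, numbers censored and the median. Neither document plans a cumulative incidence function.

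SAP 10.2 then has one paragraph per reason:

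- Lack of efficacy: "evaluated as described above only for subjects who discontinued due to lack of efficacy", followed by "subjects who discontinue IMP for reasons other than lack of efficacy will be censored at the time of discontinuation".
- Adverse events: "evaluated as described above only for subjects who discontinued due to AEs", followed by "subjects who discontinue the IMP for reasons other than AE will be censored at the time of discontinuation".
- Opioid no longer needed: no restriction on who is analysed, only "subjects who discontinue IMP for other reasons will be censored at the time of discontinuation".

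SAP 7.2.1 explains why the third analysis was added for the Tapentadol Period: "as this is one of the main reasons for discontinuation of treatment of Part 2".

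**The concern.** There are two separate difficulties.

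The first is textual. In the lack-of-efficacy and adverse-event paragraphs, one sentence limits the analysis to subjects who had the event and the next censors subjects who did not. A programmer at the contract research organization could follow either sentence and would get a different curve and median.

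The second remains after the text is repaired. Censoring a subject who stopped for another reason treats that subject as still liable to stop later for an adverse event or lack of efficacy. Someone who is off the drug cannot do so. One minus Kaplan-Meier therefore exceeds the proportion who actually stop for the reason in question, and the reason-specific figures need not add up to overall discontinuation.

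At stake is the description of how long children stay on tapentadol and why they stop. The stated objective of Part 2 is the long-term safety profile.

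**Working it through.** **The text.** If only subjects with the event are analysed, nobody is left to censor, so the sentences quoted from the lack-of-efficacy and adverse-event paragraphs would do nothing. The base rule in SAP 18.1.4.1, which censors treatment completers, would do nothing either. The third paragraph has the same structure without the restriction. The coherent reading is that all subjects of the period are in the risk set and the restricting phrase is a leftover.

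**Inputs for the size.** The documents give no discontinuation rate and no split by reason, so there is no planned figure to reproduce. All rates below are assumptions. The only guidance on level is qualitative:

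- SAP 7.2.2 describes discontinuation in the Treatment Period as very low.
- SAP 7.2.1 names opioids no longer being needed as a main reason for stopping in Part 2.
- Protocol 8.4 cites a similarly designed pediatric trial in which few subjects stayed on medication beyond one month.

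**Formulas.** Assume constant hazards. Let P be the total proportion stopping by the end of the period and s the share of stops for the reason of interest.

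- Total cumulative hazard: H = −ln(1 − P)
- One minus Kaplan-Meier, other stops censored: 1 − exp(−sH)
- True cumulative incidence: sP

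**Scenario A: 15% of stops are for adverse events.**

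- P = 80%: H = 1.609 and sH = 0.2414. One minus Kaplan-Meier is 1 − exp(−0.2414) = 21.4%; the truth is 0.15 × 80% = 12.0%.
- P = 90%: H = 2.303 and sH = 0.3454. One minus Kaplan-Meier is 29.2%; the truth is 0.15 × 90% = 13.5%.

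In both cases the true proportion is above 10%, so the reason-specific trigger is met.

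For additivity at P = 80%, group all other reasons together (s = 0.85): 1 − exp(−0.85 × 1.609) = 74.5%. The two estimates sum to 21.4% + 74.5% = 95.9%, against 80% who stop.

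**Scenario B: 12% truly stop for the reason of interest.**

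| Stop for other reasons | One minus Kaplan-Meier | Ratio to the true 12% |
|---|---|---|
| 5% | 12.3% | 1.03 |
| 20% | 13.5% | 1.12 |
| 40% | 15.6% | 1.30 |
| 60% | 19.1% | 1.59 |

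For the 40% row: P = 52%, H = −ln(0.48) = 0.734, s = 12/52, sH = 0.1694, and 1 − exp(−0.1694) = 15.6%.

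**Simulation check (4,000 runs, assumed rates), one minus Kaplan-Meier against Aalen-Johansen cumulative incidence.**

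- Tapentadol Period, 60 subjects, 12% for the reason and 62% for others: 19.6% against 12.0%.
- Same size, 12% and 35%: 14.8% against 11.9%.
- Part 1, 46 subjects, 12% and 5%: 12.4% against 12.1%.

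The excess is small in Part 1 and grows with the amount of competing discontinuation.

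**The case against.** The strongest reply is that censoring other reasons is a standard cause-specific description. The bias appears only if one minus Kaplan-Meier is read as the absolute probability of stopping for that reason, and the SAP never says it will be. This stands in part: Kaplan-Meier can describe a hypothetical setting without other stops. But the SAP states no such target, and that reading would need the other stops to be independent of the event. SAP 18.1.3 says subjects leave tapentadol because the pain has improved or the disease has worsened, which ties the reason for stopping to the course of pain.

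A second reply is that the absolute figures exist elsewhere. For adverse events this largely holds: SAP 15.1.2.1 tabulates the number and percentage of subjects with a treatment-emergent event leading to discontinuation of study drug. For lack of efficacy, the reasons table in SAP 10.2 uses discontinuers as denominator, so a reader must divide its counts by the number entering the period. Once all subjects have been followed to the end of Part 2, that crude proportion is essentially the cumulative incidence. At the interim analysis of Part 2 (SAP 6.1), with subjects still on treatment, it is not.

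Two stronger readings are tempting, and the documents do not support them:

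- A reader might infer that the planned curves will reach 100% by construction, since only subjects with the event are analysed. The adjoining censoring sentences and SAP 18.1.4.1 contradict that, so it is an ambiguity to remove and not a planned result.
- A reader might infer that these curves appear once more than 10% stop for any reason. That is the trigger for the overall analysis. Each by-reason analysis is naturally read as needing more than 10% to stop for that reason. If 50% stopped with 15% of stops for adverse events, 0.15 × 50% = 7.5% would stop for adverse events and no adverse-event curve would be produced.

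**Conclusion.** The point holds as a wording contradiction plus a bias of known direction. The contradiction is certain from the text. The direction of the bias is mathematical: one minus Kaplan-Meier with other stops censored is never below the cumulative incidence, and it is above it whenever a competing stop precedes an event of interest.

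The size is not fixed by the documents. Under the assumed constant hazards the overstatement is about 10% in relative terms with 20% competing stops and about 60% with 60%. It is roughly twofold in the heaviest-attrition scenario (29.2/13.5 = 2.2). It is material only in the Tapentadol Period.

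Importance is limited. The analysis is descriptive, conditional on a threshold and attached to an other endpoint, with no test planned. The primary endpoint and sample size are untouched. It is still worth correcting, because the protocol itself calls for these analyses.

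**What to change.** In SAP 10.2:

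1. Delete the restriction to subjects who discontinued for the given reason from both the lack-of-efficacy and the adverse-event paragraphs.
2. State the risk set: all Safety Set subjects by treatment group for Part 1, and all subjects entering the Tapentadol Period for Part 2.
3. For lack of efficacy, adverse events and opioid no longer needed, report the Aalen-Johansen cumulative incidence with confidence intervals, treating the other reasons as competing events.
4. Keep Kaplan-Meier for discontinuation of study drug for any reason, and adjust SAP 8.1 so that it no longer prescribes Kaplan-Meier for every time-to-event variable.

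The cost is a few sentences in the SAP and one procedure option in the program. No new data are needed. The general wording of Protocol 14.2.6.4 already accommodates the change.
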